A study binder will be kept by the research coordinator/enrollers that will record the names and unique identification code of each patient approached for enrollment in an enrollment log. The names and demographic information (age, gender, Hb-genotype) of those who were approached and decline enrollment and the reason for declining (if known) will be recorded as approached/not enrolled. Age, gender and Hb-genotype information on patients screened by the study team/coordinator but found to be not eligible will also be collected. All study binders will be kept in a locked cabinet in the research office of the PED or Aflac coordinators and electronic files with any private health information (PHI) will be kept in a password protected CHOA supported division sharepoint site that is backed up nightly. Only members of the study team will have access to the study folder.

Randomization and Arginine/Placebo Administration

Arginine/Placebo will be administered in a blinded fashion. Using randomization lists prepared by the

research pharmacist, the research pharmacist at Egleston Children's Hospital will perform a block randomization for all CHOA sites, and study drug will be allocated to the patient TID until discharge. **Randomization will be stratified for hydroxyurea use to insure an equal number of patients on HU in all arms to minimize this as a potential confounder.** The patient, nurses, and physicians caring for the patient will be blinded as to which medication the patient is receiving.

Once written informed consent is obtained, and eligibility is confirmed by study staff, children and adolescents age 3-21 years will be randomized to one of following three study arms:

- 1) Standard L-arginine dose (100mg/kg IV TID)
- 2) One-time L-arginine loading dose (200mg/kg IV) plus the standard dose (100mg/kg IV TID)
- 3) Placebo (normal saline 1-2 ml/kg IV TID)

Upon enrolment, the patient's medical record is reviewed for CMP and creatinine testing in the past month in the past 12 months.

- If there are no measurements within the past 12 months or if either SGPT/ALT or creatinine were elevated in the past 12 months (meeting exclusion criteria), the current CMP results must be reviewed prior to dose administration. (Patient may be randomized; however, delivery of study drug should be held until CMP results are reviewed and no exclusion criteria are noted).

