The primary goal of this analysis is to compare the standard arginine treatment with placebo. The power analysis is based on this comparison. This sample size calculation is based on a two-sample two-sided t-test, with the objective of detecting a 55% reduction in opioid use from its mean value (4.1) in the placebo group based on the preliminary data generated from the recent [name] arginine trial (1). Based on these findings, the standard deviations are 2.0 and 4.1 (days) in the arginine and the placebo groups, respectively. A sample size of 33 subjects per group has 80% power to detect the treatment effect stated above on a two-sided test at the 0.05 significance level. A secondary goal is to compare the other arginine treatment arm (with a loading dose) to the placebo arm. Finally the two arginine treatments will be compared to determine if there is any difference or trend towards a difference when a loading dose is used that is superior to the standard arginine dose used with success in prior studies. Based on past experiences with arginine therapy, few patients withdrew from the study after the therapy was switched from oral to parenteral. Up to 150 patients will be enrolled, allowing for screen failures and study withdrawal, in order to insure randomization and study completion of 108 patients (36 per group) allowing for a 7% withdrawal rate. We did not adjust the sample size calculations for multiple comparisons as the power calculation only corresponds to the primary goal involving a single comparison of patients receiving the standard treatment or the placebo. We anticipate that the "loading dose" arm will be either the same or better than the standard dose. We will evaluate the efficacy and safety of this loading dose compared to the placebo group.

Each of the comparisons mentioned above will be conducted via a general linear model analysis. Predictors will include the treatment indicator, use of HU, age group, gender and the interactions of each of the last three covariates with the treatment indicator. By including interactions in the model we will be able to determine whether the treatment effect varies across subgroups of patients.

Assistance with statistical analysis and power calculation was provided by the Department of Biostatistics and Bioinformatics at the Rollins School of Public Health, Emory University, by [name] PhD, who will be the biostatistical consultant on this project.

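### The primary model contains three treatment interactions, and the plan does not name the contrast that tests standard arginine against placebo overall

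*Combined protocol and SAP*

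**What the plan says.** All of this is in the Statistical Analysis section unless noted.

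- Goal: "The primary goal of this analysis is to compare the standard arginine treatment with placebo". The power calculation is said to correspond to "a single comparison of patients receiving the standard treatment or the placebo".
- Sizing: "This sample size calculation is based on a two-sample two-sided t-test", aimed at "detecting a 55% reduction in opioid use from its mean value (4.1) in the placebo group". The plan gives 33 per group for 80% power and expects 36 per group to complete.
- Analysis: "Each of the comparisons mentioned above will be conducted via a general linear model analysis". Besides treatment, the predictors are "use of HU, age group, gender and the interactions of each of the last three covariates with the treatment indicator".
- Purpose of the interactions: "By including interactions in the model we will be able to determine whether the treatment effect varies across subgroups of patients".
- Under Randomization and Arginine/Placebo Administration: "Randomization will be stratified for hydroxyurea use to insure an equal number of patients on HU in all arms". Age group and gender are not stratified.

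The plan gives no covariate coding or centring, no age-group cut points, no weighting for an overall effect, no rule for dropping interactions and no model without them. The t-test appears only in sample size calculations.

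**The concern.** Once treatment interacts with HU, age group and gender, the model yields a different treatment effect for each combination of the three. An overall effect exists only after a weighting is chosen. Two weightings are in ordinary use: averaging over the covariate distribution observed in the trial, or giving each level of each covariate equal weight, as least-squares means commonly do. They are different tests, with different standard errors and p-values on the same data.

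Two analysts who both follow the plan could therefore report different primary results, and the choice could be made after the data are seen. If the true effect varies by subgroup, the two averages also estimate different quantities. The interactions are there to describe subgroups, and that purpose does not require them in the primary test.

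**Working it through.** **Inputs from the plan.** Difference 0.55 x 4.1 = 2.255 mg/kg; SDs 2.0 (arginine) and 4.1 (placebo); two-sided alpha 0.05; 36 completers per arm. The SDs are labelled as days, but they match the pilot's mg/kg standard errors with 26 per arm: 0.4 x √26 = 2.04 and 0.8 x √26 = 4.08.

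**Inputs assumed.** The plan gives no covariate proportions for this trial. I took HU and two age groups from 50/50 to 70/30, with gender near 50/50 because the pilot was 52% female. HU is balanced between arms by stratification; age group and gender vary by chance. The true effect is the same in every subgroup and the covariates do not predict outcome.

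**Step 1: the plan's own figure.** SE = √[(2.0² + 4.1²)/n] = √(20.81/n).

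- n = 33: SE 0.794, ratio 2.255/0.794 = 2.84, t-test power 80%. The stated figure reproduces.
- n = 36: SE 0.760, ratio 2.97, power 83%.

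**Step 2: why the weighting matters.** Every covariate interacts with treatment, so the model amounts to a separate regression in each arm. The variance of an arm's predicted mean at covariate values m is σ²[1/n + (m − c̄)′S⁻¹(m − c̄)], where c̄ holds the arm's covariate means and S its centred cross-products.

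- Observed average: m lies close to c̄ in both arms, so the second term is small.
- Equal weights: m = 0.5 for each binary covariate. Ignoring chance imbalance, the variance is multiplied by about 1 + Σ(0.5 − p)²/[p(1 − p)]. A 70/30 split adds 0.04/0.21 = 0.19.

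At n = 36, the equal-weight contrast then gives:

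- HU 70/30 only: SE 0.760 x √1.19 = 0.830, ratio 2.72, power about 76%.
- HU and age 70/30: SE 0.760 x √1.38 = 0.893, ratio 2.52, power about 70%.

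**Step 3: with chance imbalance in age and gender.** Design matrices were drawn at random, each contrast's true variance was computed, and noncentral-t power was averaged over the draws (residual df 72 − 8 = 64 with interactions, 67 without). At 36 per arm, gender 50/50:

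| HU split | Age split | Observed average | No interactions | Equal weights |
|---|---|---|---|---|
| 50/50 | 50/50 | 82% | 82% | 81% |
| 60/40 | 50/50 | 82% | 82% | 79% |
| 60/40 | 60/40 | 82% | 82% | 77% |
| 70/30 | 50/50 | 82% | 82% | 74% |
| 70/30 | 70/30 | 82% | 82% | 67% |

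**Step 4: how often the verdict changes.** In simulated trials with the same true effect in every subgroup, the observed and equal-weight averages disagreed at p < 0.05 in about 3% of trials (all splits 50/50), 12% (HU 70/30) and 18% (HU and age 70/30). The observed average and the model without interactions disagreed in about 1%.

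**Step 5: different quantities.** As an invented illustration, take an effect of 1.5 mg/kg with HU and 3.0 without, with 70% on HU. The observed average is 0.7 x 1.5 + 0.3 x 3.0 = 1.95; the equal-weight average is (1.5 + 3.0)/2 = 2.25.

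**The case against.** The strongest reply is that any competent analyst would average sensibly, and that the planned power is then intact. The second half is right: the observed average has about 82% power, so the interactions cost almost nothing if that contrast is named. The first half does not settle the matter, because both averages are sensible.

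The size of the shortfall is also open to challenge, and much of that challenge stands:

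- The splits are assumed. With milder ones the loss is small: 79% at HU 60/40. Stratifying on HU balances it between arms but does not make HU use 50/50.
- Some would count all 38 randomized per arm, since the protocol refers to intention-to-treat. With HU and age both 60/40, equal-weight power is then about 80%.
- Stratifying on HU as a potential confounder suggests that it is prognostic, and the planning SDs are unadjusted. If covariates explained 10% of the variance, equal-weight power at HU 70/30 would be about 79%. If they explained 20%, it would be about 77% with HU and age both 70/30. The absolute figures above are therefore pessimistic. The observed average gains as well, to about 86% and 90% respectively, so the gap stays.

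Three stronger readings are tempting. A reader might infer that the trial is underpowered; the documents do not support that, since the stated sample size reproduces and two natural contrasts keep the planned power. A reader might quote equal-weight power near 60%; that needs a 70/30 gender split on top of the others, and the pilot, the only evidence in the documents, was 52% female. A reader might also infer that the treatment coefficient under 0/1 coding will be reported, which would be the effect in one reference subgroup. The plan states no coding and does not say this term will be read, and its stated goal is an overall comparison.

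**Conclusion.** The point holds as an unnamed primary contrast. That part rests on the text alone: one overall comparison is promised, and the only model offered for it has no single treatment effect. The consequence is conditional. At 36 per arm, power is about 82% for the observed average or the model without interactions, against about 67-81% for equal weights. This assumes HU and age splits from 50/50 to 70/30, gender near 50/50, a common true effect and non-prognostic covariates. Relaxing the last assumption raises all the figures without closing the gap. The choice can change the primary verdict, so it should be fixed before the results are seen. The sample size does not need to change.

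**What to change.** Name the primary contrast in the Statistical Analysis section. Either of these would do:

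- State that the primary test and 95% CI for standard arginine against placebo are the treatment effect from a general linear model with treatment, HU stratum, age group (cut points stated) and gender, without interactions. Fit the three treatment interactions in secondary models, reported as subgroup analyses.
- Keep the interactions and state that the primary test is the treatment effect averaged over the observed covariate distribution, with covariates centred at their sample means. State the age cut points here too.

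Power is about the same under either, so the essential step is to name one. Apply the same rule to the two other comparisons, loading dose against placebo and loading dose against standard dose. The cost is one or two sentences, with no extra patients or data and no material loss of power.
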